Appendix 5d (contd)
INTERNATIONAL CENTRE FOR DIARRHOEAL DISEASE RESEARCH, BANGLADESH
Studies to enhance and improve immunogenicity of cholera and enterotoxigenic *E. coli* (ETEC) vaccines
Adverse Events

Report all adverse events which occurred from the beginning of the study up to the end

Serious/Life-threatening adverse events are the following :

- death,
- life-threatening events,
- hospitalization or prolongation of hospitalization,
- disability,
- congenital anomaly,
- occurrence of malignancy.

Adverse event severity definitions :

Mild : Adverse event usually transient in nature and generally not interfering with normal activities.

Moderate : Adverse event causing sufficient discomfort to interfere with normal activities.

Severe : Adverse event which is incapacitating and prevents normal activities.

In case of occurrence of adverse events, even if treatment is discontinued, the observation will be considered as complete only when all of the information mentioned above is collected.

Relation to vaccine - Definition :

None: No relation to administration of the study vaccine, i.e. existence of a clear alternative explanation, an unreasonable temporal relationship between the vaccine and the event, non-plausibility.

Remote: A clinical including a laboratory test abnormality, with a temporal relationship to vaccine administration which makes a causal relationship improbable, and in which other drugs, chemical or underlying disease could provide explanations.

Possible: A clinical including a laboratory test abnormality, with a reasonable time sequence in relation to administration of the study vaccine, but which could also be explained by concurrent disease or other drugs or chemicals.

Probable: A clinical event, including a test abnormality, with a reasonable time sequence in relation to administration of the study vaccine, unlikely to be attributed to concurrent disease or other drugs or chemicals, and which shows a satisfactory clinical course following withdrawal.

Highly Probable: A report suggesting an adverse reaction which cannot be evaluated because information is insufficient or contradictory, and which can neither be supplemented nor verified. Evaluation of the relationship enabling classification between the above items should nevertheless be attempted, with the outcome of the event being taken into consideration.

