Our recent studies have shown zinc enhances the antibacterial antibody responses in toddlers (2-5 years of age) given the oral killed cholera or the ETEC vaccine. We hope that it will also have an effect of improving the immunogenicity in younger children 6-24 months of age who are given the cholera or ETEC vaccine. For this purpose we will supplement children 6 months -2 years of age with daily zinc sulfate (10 mg/day) for two weeks prior to immunization and for the duration of the study. Two doses of the oral killed vaccine will be given two weeks apart and studies continued until a week after the second dose. Thus the study will be undertaken for a period of about 5 weeks in total. A comparison group will be given the vaccine two weeks apart without any zinc supplementation.

Sample size- A total number of 300 children will be studied (75x2= 150 for ETEC vaccine related; 75x2= 150 for cholera related groups for 2 vaccines, with and without zinc).

Time frame: Within 6 month -2 years of the initiation of the study.

Overall design for the vaccine studies:

The vaccine studies will be carried out at the Mirpur field site in urban Dhaka. For both the cholera and ETEC vaccines, two doses will be given 14 days apart. The reactogenicity will be monitored for 3 days after intake of each dose of the vaccine. In the case of the children 6 months to 2 years of age, active surveillance will be carried out by the field staff in the homes by visits every day for 3 days after intake of the vaccine. Since the ETEC and cholera vaccines have generally been found to be safe at the doses being used, passive surveillance has been used in most studies in the case of both adults and children carried out so far. We are however using more precaution by carrying out active surveillance for the children.

Blood and stool samples will be collected prior to immunization and 7 days after intake of each dose of the vaccines in volumes indicated for the immunological assays (Appendix-1-7). They will not be allowed to eat or drink one hour before and after intake of the vaccine except where specified where the duration will be longer. Only when the effect of breast feeding on the immunogenicity of the cholera and ETEC vaccine will be studied the children will be withheld from breast feeding for 3 hours prior to and one hour afterwards. They can drink water during this period.

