Baseline evaluation of samples:

Stool examination: A routine stool microscopic examination and culture for *V. cholerae* O1/O139 and ETEC will be carried out four days prior to vaccination. Children whose stools are positive for these pathogens will not be vaccinated since this will interfere in the evaluation of the response to the vaccine. When immunization for the second dose of the vaccine will be carried out (14 days after the first dose) children who have fever or diarrhoea will be excluded from the study.

Zinc: Serum zinc concentrations will be determined at baseline only. Venous blood collected in trace element free vacutainers will be placed in ice until arrival at the ICDDR,B laboratory on the same day. Serum will be assayed by flame atomic absorption spectrophotometry and zinc deficiency will be defined as a serum zinc concentration <60 ug/dl (31).

Vaccine, administration and allocation: Both the cholera and ETEC vaccine are produced by the Swedish Bacteriological Laboratories (SBL Vaccin AB Stockholm, Sweden). One dose of the ETEC vaccine contains 1.0 mg BS plus 2×10^{10} formalin inactivated bacteria each of 5 strains of ETEC expressing 6 colonization factors. The oral inactivated cholera vaccine (Dukoral) consists of killed bacteria prepared from individual batches of O1 El Tor and classical *V. cholerae* to include both LPS and protein antigens and also contains recombinant BS. One dose of vaccine contains 1.25×10^{11} CFU of the killed whole cell vaccine plus 1 mg of BS developed in Sweden and also produced by SBL. New batches of ETEC vaccine containing 1.0 mg of BS plus about 10^{11} formalin inactivated bacteria expressing colonization factors will be prepared for the study. For all children a quarter dose of the CF-BS-ETEC vaccine will be tested since some adverse events of vomiting was observed with the higher dose (Qadri et al. in manuscript).

Informed written consent will be taken from the parent/guardian for the children for the immunization and for the permission to draw blood and obtain stool samples (Appendices).

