Appendix 5d

INTERNATIONAL CENTRE FOR DIARRHOEAL DISEASE RESEARCH, BANGLADESH
 Studies to enhance and improve immunogenicity of cholera and enterotoxigenic *E. coli* (ETEC) vaccines
adverse event form
Surveillance After Vaccination

Random # **Investigator** **Initials of participants** **Inpatient**
Number

Were there any adverse events associated with administration, whether or not they were considered vaccine-related?
 If yes, please complete all sections below (circle appropriate number) 1=No & 2=Yes.

Adverse events, specify: Please list one event per line	Serious Including Life-threat 1=No 2=Yes	Start Date		Stop Date		Severity 1=Mild 2=Moderate 3=Severe	Relation to Study Vaccine 1=None 2=Remote 3=Possible 4=Probable	Therapy Required 1=No 2=Yes (specify below) 5=Highly Probable	Outcome 1=Resolved 2=Improved 3=Unchanged 4=worsened 5=Follow up not done
		dd	mm	yy	dd				
	1 2					1 2 3	1 2 3 4 5	1 2	1 2 3 4 5
	1 2					1 2 3	1 2 3 4 5	1 2	1 2 3 4 5
	1 2					1 2 3	1 2 3 4 5	1 2	1 2 3 4 5

Further details of adverse events and classification of above entries (specify dates and include information on concomitant medications and concurrent conditions)

--

Date.....

Investigator's signature.....

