Appendix-7

^aZinc supplementation started at d-10 (10 days prior to first vaccine dose)

^b2 doses of vaccine at day 0 and day 14

^cBlood draw and stool samples collected at day 0, day 7 and day 21

Personnel	Position	Rate	Effort %	Salary	1st Year US\$	SEK	2nd Year US\$	SEK	3rd Year US\$	SEK	TOTAL US\$	SEK
-----------	----------	------	----------	--------	------------------	-----	------------------	-----	------------------	-----	---------------	-----

Please note, the funds below from the ICDDR,B consumable component will be kept in Goteborg for purchasing reagents for ICDDR,B

[figure not shown]
2000	14,895	1,200	8,937	1,800	13,405	5,000	37,237
------	--------	-------	-------	-------	--------	-------	--------

Total funds needed for study for ICDDR,B and Goteborg University

Total funds needed for study for ICDDR,B and Goteborg University		1st Year		2nd Year		3rd Year		TOTAL	
		US\$	SEK	US\$	SEK	US\$	SEK	US\$	SEK
ICDDR,B		59,082	440,000	59,753	444,998	71,166	529,995	190,001	1,414,993
Goteborg University		24,170	180,000	17,456	130,003	29,541	220,000	71,167	530,003
Total Sida-SAREC		83,252	620,001	77,209	575,001	100,707	749,995	261,168	1,944,996

(Please note, the funds below are included in the budget above in the ICDDR,B component for purchasing reagents for ICDDR,B

2,000	14,895	1,200	8,937	1,800	13,405	5,000	37,237
-------	--------	-------	-------	-------	--------	-------	--------

 [name]
 Director
 Bangladesh

International Centre for Diarrhoeal Disease Research, Bangladesh
CENTRE FOR HEALTH AND POPULATION RESEARCH
Mail : ICDDR,B, [name]
[contact], Telex : [name]
[contact], [name]
Cable : Cholera Dhaka

Memorandum

23 November 2004

To : [name]
Principal Investigator of research protocol # 2004-046
Laboratory Sciences Division (LSD)

From: [name]
Chairman
Research Review Committee (RRC)

Sub : Approval of research protocol # 2004-046

Thank you for your memo dated November 21, 2004 with the modified version of your research protocol # 2004-046 titled "Studies to enhance and improve immunogenicity of cholera and enterotoxigenic *E. coli* (ETEC) vaccines". The issues that were raised by the RRC in its meeting held on November 9, 2004 on your research protocol have been addressed in the modified version of the protocol to the satisfaction of the Committee. Accordingly, the Committee approved the research protocol to proceed subject to the approval of the ERC.

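### The Probable causality grade in Appendix 5d requires a good course after withdrawal, which does not suit a two-dose oral vaccine and makes causality depend on outcome

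*Protocol*

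**What the plan says.** The definitions page of Appendix 5d sets out five grades of relation to vaccine: None, Remote, Possible, Probable and Highly Probable. Probable asks for reasonable timing and then for an event "unlikely to be attributed to concurrent disease or other drugs or chemicals, and which shows a satisfactory clinical course following withdrawal". The conditions are joined by 'and', with no exception for cases where withdrawal is impossible.

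The grade below, Possible, also asks for reasonable timing, "but which could also be explained by concurrent disease or other drugs or chemicals". The grade above, Highly Probable, is defined as "A report suggesting an adverse reaction which cannot be evaluated because information is insufficient or contradictory", followed by the instruction "Evaluation of the relationship enabling classification between the above items should nevertheless be attempted, with the outcome of the event being taken into consideration".

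The exposure being graded is the vaccine. The overall design section states "For both the cholera and ETEC vaccines, two doses will be given 14 days apart", and Appendix 7 gives the same schedule ("doses of vaccine at day 0 and day 14"). The baseline evaluation section adds that, when the second dose falls due, "children who have fever or diarrhoea will be excluded from the study".

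The Appendix 5d form has separate columns for seriousness, severity, relation to study vaccine and outcome. The outcome codes include "1=Resolved 2=Improved 3=Unchanged 4=worsened". The definitions page lists death and disability among the serious events.

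**The concern.** A requirement that the event settles after withdrawal makes sense for a drug that is taken daily and can be stopped. A swallowed vaccine dose cannot be taken back. After the first dose, the most that can happen is that the second is not given; after the second, nothing is left to withhold.

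The larger difficulty is that the condition brings outcome into a judgement about cause. Whether a reaction was brought on by the vaccine and whether the child recovered are separate questions, and the form already has a column for the second. Under the stated rule, two events alike in timing and in the absence of a likely alternative cause are graded differently because one resolved and the other did not, and it is the one with the bad outcome that loses the Probable grade. A listing of vaccine-related events that starts at Probable would therefore leave out non-recovering events by definition.

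**Working it through.** No figure in the protocol is involved and no arithmetic applies, so the check is a logical one: take a test event and try it against each grade.

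**Test event.** Reasonable timing after a dose, biologically plausible, unlikely to have another cause, and ending in death or coded as unchanged or worsened.

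| Grade | What the definition needs | Does the test event fit? |
|---|---|---|
| None | A clear alternative explanation, unreasonable timing, or implausibility | No |
| Remote | Timing that makes causation improbable, with other explanations available | No |
| Possible | Reasonable timing, and another cause that could also explain the event | Only if some other cause, though unlikely, could still explain it |
| Probable | Reasonable timing, other causes unlikely, and a satisfactory course after withdrawal | No: it fails the last condition |
| Highly Probable | A report that cannot be evaluated | No: the test event can be evaluated |

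**Two readings of withdrawal.**

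1. Literal: the vaccine is withdrawn. After the second dose this cannot happen, so no event then could meet the condition, whatever its outcome.
2. Loose: withdrawal means that exposure has ended. Events that settle then meet the condition, and events that do not settle fail it.

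The test event fails Probable on both readings. The dependence on outcome comes from the loose reading, which is the only one that leaves the grade usable after the second dose.

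**Could anything else on the page rescue it?** The instruction that closes the Highly Probable definition asks for classification to be attempted with outcome in mind. That gives the assessor some discretion, but it does not lift the condition in Probable, and it adds a second route by which outcome enters the grade. Nor does the zinc supplement, which is taken daily and could be stopped, alter the reading: the column grades relation to the study vaccine.

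**Effect of deleting the clause.** Probable would then need reasonable timing and other causes unlikely. The test event meets both, and its outcome still appears in the outcome column.

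**Where the grade is used.** The safety end point section defines the primary safety end point as occurrence of diarrhoea, vomiting or abdominal cramps of at least moderate grade, with no causality test. The data analysis section compares overall rates of adverse reaction and sets no causality cut-off.

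**The case against.** The strongest reply is that little in the plan turns on this grade. The form collects events whether or not they are thought to be vaccine-related, the definitions page asks for all adverse events to be reported, and seriousness, severity and outcome each have their own column. The primary safety end point ignores the grade. All of this stands, and it sets the limit on the point.

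Three stronger readings are tempting, and the documents do not support them.

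- *One arm could look safer than another because its reactions are slower to resolve.* This needs a between-arm count restricted to Probable or above. The protocol specifies none.
- *The Safety Monitoring Committee would not see the worst events.* Nothing in the protocol makes what reaches the committee depend on the causality grade. The label would be wrong; the event would still be on record.
- *The worst reactions have no valid grade at all.* Unlikely to be due to another cause and could also be explained by another cause are not opposites, so some of these events fit Possible. The gap is complete only where no other cause is conceivable, and then partly because Highly Probable carries the wrong wording, which is a separate defect.

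A reader might also measure the problem by the number of planned second doses. That counts doses, not misgraded events, and says nothing about how often the clause would bite.

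Two matters of scope also stand. Disability is a criterion of seriousness, not an outcome code, so a disabling event that recovers is not barred. And the definitions sit with form 5d; the day 1 to 3 follow-up form in Appendix 5c has its own four-level relation item, without Remote, and is not expressly linked to them.

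**Conclusion.** The point holds in a limited form. As worded, Probable contains a condition that does not suit two single oral doses and that makes causality depend on outcome. An event with reasonable timing and no likely alternative cause that ends in death, or stays unchanged or worsens, cannot be graded Probable. It is downgraded to Possible where another cause could conceivably explain it, and otherwise has no fitting grade until Highly Probable is corrected as well.

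The harm is confined to the causality grade on form 5d and to any vaccine-related summary built on it. Recording of the event and the primary safety end point are unaffected. How many events would be misgraded cannot be estimated, because the protocol gives no expected rate of fatal or unresolved events. The conclusion assumes that assessors apply the definitions as written; one who ignores the clause would avoid the error, but the page gives no authority for doing so. Because the protocol itself fixes this definition, it is not a matter left to a statistical analysis plan.

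**What to change.** In the Probable definition of Appendix 5d, delete the words from 'and which shows' to 'following withdrawal'. State that causality is graded on timing, plausibility and alternative explanations only, and that outcome is recorded solely in its own column.

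In the same edit, reconcile the Highly Probable definition: give the top grade a definition that an assessable event can meet, and remove the instruction to take outcome into consideration. Correcting Highly Probable alone would leave the clause in Probable in place; deleting the clause alone would leave the top grade unusable. While the page is open, align the relation scale on form 5c with the one on form 5d.

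The cost is a few lines of form wording. It needs no extra data, visits or children, and changes no dose or clinical rule.

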Although the study is an open design, the clinician in the field will code the samples before sending them to the laboratory so that the laboratory personnel will be blinded when the analyses are carried out. The laboratory will only know if the samples have to be analyzed for the cholera or the ETEC vaccine immunological responses.

Samples from vaccines that will be collected at 3 time points will be tested for antibody responses. From blood PBMC will be separated for preparation of antibody in lymphocyte supernatants (ALS, Qadri et al. 2003). ALS and serum samples collected from vaccines at the preimmune (day 0) and post-vaccination days (day 7 and day 21) will be tested for antibody responses. ALS and sera from vaccinees receiving the CF-BS-ETEC vaccine or the cholera vaccine will be tested for the IgA antibody responses to different antigens including (for ETEC CFA/I, CS1,CS2,CS3,CS4,CS5, for cholera vaccine to LPS and to CTB for both). Using fecal extracts from the vaccinees at the 3 time-points, IgA antibody responses to CFA/I, V. cholerae O1 LPS and CTB will be measured. These procedures are already set-up in the laboratory of the investigators (Qadri et al. 2000,2003). Further to test the immunogenicity of the cholera vaccine we will test the vibriocidal antibody response at the 3 time points mentioned above as well as the response to LPS (O1 Ogawa and Inaba) using sera. In addition, the IgA and IgG antibody responses to rCTB will be measured in those being immunized with the cholera or the ETEC vaccine. The serum zinc level will also be assessed at the baseline in all the children since it may have an effect on the response to the intervention(s) and the vaccination.

Safety Monitoring Committee

[name] (CSD) will serve as the Chairperson of the committee. Other members include [name].(CSD), [name] (CSD) and [name] (LSD). The members are in no way involved with the project.

Safety endpoint and safety evaluation

The primary end point for evaluating safety will be defined as the occurrence of any of the following diarrhoea, vomiting or abdominal cramps of at least moderate grade. Diarrhea will be defined as three or more loose or liquid stools in any 24-h period. A measured oral or rectal temperature above 38°C will be considered a fever.

Overall laboratory tests for the project

Vaccinees:

Stools will be cultured on MacConkey agar and tested for colonization factors of ETEC by dot blot immunoassay

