Appendix 5c

INTERNATIONAL CENTRE FOR DIARRHOEAL DISEASE RESEARCH, BANGLADESH
Studies to enhance and improve immunogenicity of cholera and enterotoxigenic *E. coli* (ETEC) vaccines:
Post vaccination adverse event follow up form
Surveillance After Vaccination

63. Primary vaccination

64. Date
DD MM YY

65. Day 1/ Day 2/ Day 3

66. Completeness of dosing 1 = Yes 2 = No

67. Amount ingested: 1=100% 2= \geq 90% 3= $<$ 90%

LOCAL REACTION (68 - 73)

68. Abdominal pain 1= No 2=Mild 3= moderate 4=severe	69. Distension 1=No 2= moderate 3= severe
70. Vomiting 1=No 2= Yes If yes,	71. Number/day  / day
72. Diarrhoea [$>$ 3] watery or loose stool] 1=No 2= Yes If yes,	73. Number/day  / day

SYSTEMIC REACTION (74 - 81)

74. Fever (Axillary temp $>$ 37.8°C) 1= No 2= Yes	75. If yes, temperature (°C)   .  
76. Loss of appetite/ Poor feeding 1= No 2= Yes	77. Irritability 1= No 2= Yes
78. Nausea 1= No 2= Yes	79. Dizziness 1= No 2= Yes
80. Exanthema 1= No 2= Yes	81. Other 1= No 2= Yes

82. Relation to vaccine: 1 = None 2 = Possible 3 = Probable 4 = Highly probable

83. Therapy required 1= No 2= Yes

84. Outcome 1 = resolved 2 = improved 3 = unchanged 4 = worse

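### The top causality grade carries the definition of an unassessable report, forms 5c and 5d number causality differently, and form 5c does not collect the fever that the safety section defines

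*Protocol*

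**What the plan says.** **Causality definitions.** Appendix 5d (contd) defines None, Remote, Possible, Probable and Highly Probable. The last reads: "Highly Probable: A report suggesting an adverse reaction which cannot be evaluated because information is insufficient or contradictory". Its next clause makes clear that the gap is permanent: "and which can neither be supplemented nor verified". After that comes an instruction to the assessor: "Evaluation of the relationship enabling classification between the above items should nevertheless be attempted". The outcome of the event is to be taken into account.

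**Causality codes.** The post-vaccination follow-up form, Appendix 5c, item 82, has: "Relation to vaccine: 1 = None 2 = Possible 3 = Probable 4 = Highly probable". The adverse event form, Appendix 5d, has: "1=None 2=Remote 3=Possible 4=Probable" and "5=Highly Probable". In the extracted text the fifth label falls in the neighbouring table column. Five numbers to circle and five definitions show that it belongs to this scale.

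**Fever.** The section on safety endpoint and safety evaluation states: "A measured oral or rectal temperature above 38°C will be considered a fever". Appendix 5c, item 74, has: "Fever (Axillary temp $>$ 37.8°C", and item 75 asks for the temperature only if item 74 is yes. Appendix 5b records temperature as normal or raised, without a threshold. Appendix 5d gives no fever definition.

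**Use of the data.** The primary safety endpoint is diarrhoea, vomiting or abdominal cramps of at least moderate grade. The Data Analysis section compares overall adverse-reaction rates by a chi-squared test with Yates correction or by Fisher's exact test, and gives no relatedness cut-off.

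**The concern.** A causality scale is useful only if its labels, definitions and numbers agree. Here the strongest label sits on the definition of a report that cannot be judged. One assessor may follow the definition and code missing information as 5. Another may follow the label and reserve 5 for convincing cases. The same event then gets different grades. The study is open, with only the laboratory blinded, so an ambiguous rule is applied by staff who can know the child's group.

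The two forms also use the same digits for different grades, and both are filled in during surveillance after vaccination. The safety section names one fever event while the form completed at home visits records another.

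At stake are any summary of adverse events by relatedness and any fever rate, in children of 6 to 24 months followed actively for 3 days after each of two doses. A grade entered under the wrong definition, or a temperature never taken at the stated site, may not be recoverable later.

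**Working it through.** The plan gives no figure to reproduce, so the check compares the texts and then asks what each mismatch could do.

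**Step 1. Label against definition.** The four lower grades run from no relation up to an event unlikely to have another cause. The fifth should be stronger still. Its text instead speaks of information that is insufficient or contradictory and cannot be completed or checked. Two gaps follow: no definition exists for causality stronger than Probable, and no code other than 5 matches an unassessable report.

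**Step 2. Code against code.**

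| Code | Form 5c | Form 5d | Same meaning? |
|---|---|---|---|
| 1 | None | None | yes |
| 2 | Possible | Remote | no |
| 3 | Probable | Possible | no |
| 4 | Highly probable | Probable | no |
| 5 | not used | Highly Probable | only on 5d |

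Three of the four 5c codes differ. The effect on a related/unrelated split depends on a cut-off that the protocol does not give:

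- If related means Possible or higher, the cut is code 2 or above on 5c and code 3 or above on 5d. If the forms are combined by number, only code 2 is misplaced.
- If related means Probable or higher, the cuts are 3 and 4, and only code 3 is misplaced.

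So one code crosses the line at either cut, and only if records are combined by number. Combining by label removes the shift. It does not supply the missing Remote level: on 5c such an event must be entered as None or Possible.

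**Step 3. Possible size of the definition error.** Assume that related means Possible or higher. Let r be the proportion of children with a correctly graded related event. Let s be the proportion whose only other claim to a related event is an unassessable one coded 5.

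- Observed rate in one group = r + s, so the bias is s.
- Bias in the difference between groups A and B = s_A − s_B.

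The documents give no value for s. If s is assumed to lie between 0% and 5%, the bias in one group is 0 to +5 percentage points; in a formulation group of 102 children, 0.05 × 102 = 5.1 children. The bias in a difference between groups ranges from 0 − 5 = −5 to 5 − 0 = +5 points, and is zero when s is equal in both groups. The 5% is an illustration, not an estimate.

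**Step 4. Fever.**

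| | Site | Threshold |
|---|---|---|
| Safety section | oral or rectal | above 38°C |
| Form 5c, items 74 and 75 | axillary | above 37.8°C |

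Because 37.8 is below 38, every axillary reading above 38°C would have its value recorded in item 75, so the threshold alone could be re-applied. The site cannot be. A child with an oral or rectal temperature above 38°C but an axillary reading at or below 37.8°C is entered as no fever, with no value. The protocol gives no conversion between sites, and forms 5b and 5d do not fill the gap.

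**Step 5. Primary safety endpoint.** Its components are diarrhoea, vomiting and abdominal cramps, with a severity criterion. Neither causality nor fever enters it.

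**The case against.** The best case on the other side has five parts.

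1. *The protocol specifies no analysis by relatedness.* This stands. The primary safety endpoint has no causality criterion, and no related-event rate is defined. A reader might infer that the main safety result is biased; the documents do not support that.
2. *The entry tells the assessor to try the other grades.* This stands in part. A reader might infer that every unassessable event ends up in the top grade, but the instruction contradicts that. It does not say what to enter when the attempt fails, and it leaves strong causality undefined.
3. *A clearly vaccine-caused event can still be graded Probable.* This stands. Under a cut at Possible or Probable it would count as related, so only the split between the top two grades is lost.
4. *Nothing says the forms are combined, still less by number.* This stands. Form 5c has one relation item per daily visit, form 5d has one line per event, and each prints its own labels. The one-grade shift is a risk, not a planned step. The absence of Remote from 5c remains either way.
5. *Fever is a secondary sign, and the forms do not contradict each other on it.* This stands. Only form 5c defines fever, so the mismatch is between 5c and the safety section. It affects the fever rate, not causality. The mismatch of site and threshold is still real.

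**Conclusion.** The point holds as a correction to the forms and one definition. The top causality grade is wrongly defined, codes 2 to 4 conflict between forms 5c and 5d, and the fever that the safety section defines cannot be derived from form 5c. Events could be misclassified by relatedness if code 5 is used as printed or if the forms are combined by number.

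The size is unknown. The range of 0 to +5 percentage points rests on an assumed share of unassessable events and an assumed cut at Possible or higher.

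Two stronger readings should not be drawn. A reader might take all 1140 children as affected, but that is the number for whom the forms may be used; only children with a relevant event can be misclassified, and that number could be near zero. A reader might also suppose that the misgraded data go to the safety committee. The protocol describes its membership and independence but not what data it receives.

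The point deserves action because the errors are certain in the text, the information may not be recoverable once forms are completed, and correction costs very little.

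**What to change.** 1. In Appendix 5d (contd), give Highly Probable a definition of strong causal evidence. Move the printed text to a separate Unassessable category with a code outside the ordered scale, and keep the instruction to attempt classification first.
2. Use one causality scale with the same labels and numbers on forms 5c and 5d, including Remote on both.
3. Reconcile the measurement site and threshold for fever between the safety section and form 5c, so that the form collects the event that the protocol defines. This review takes no position on which should be kept.

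The cost is edits to two forms and one sentence, best made before the forms are printed. Design, sample size and primary safety endpoint do not change. If forms are already in use, combine existing records by label rather than number, have events coded 5 on form 5d re-read against the new definition, and state that Remote and the protocol's fever cannot be recovered from form 5c.
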